In both countries, the areas studied are affected by armed extremist groups, but humanitarians are not targeted and Tdh has security and humanitarian access experts who ensure adequate security standards are met based on a localised risk analysis. Security management is ensured by focusing on the accessibility and acceptance of interventions including this project. In addition, the potential of armed groups moving further into the study regions provokes worries about maintaining access to water sources, which are already scarce.

[figure not shown]

Figure 2: Map of potential health care facilities assessed in a pilot phase of the h4h project in the provinces of Markala, Macina, San, and Tominian in Mali, and in the provinces of Moughon, Nayala, and Sourou in Burkina Faso.

Table 1: Health care facility information assessed during a h4h pilot phase*

Characteristic	Measure	Mali (n=60)	BF1 (n=53)	BF2 (n=48)
Number of employed staff	Median	6.0	8.0	5.0
Number of outpatients during the busiest month	Median	365.0	470.0	651.0
Total number of births during the busiest month	Median	19.0	17.0	18.0
Water source which is not directly accessible in the building	Percentage	65.0	86.8	83.3

* Due to security concerns in the facilities of the first pilot phase in Burkina Faso (BF1), a second pilot phase (BF2) took place in more accessible facilities. Both are displayed in the table.

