9 months after the intervention in both of the study arms from the cluster-randomized controlled trial with a diary approach (Table 3). Every time a pre-defined health outcome takes place at facility level, this outcome will be reported in a diary by the director of the PHCF (or someone who was appointed by the director). No patient names or birth dates will be recorded to keep this data fully anonymous. For each health outcome the director will report when it happened, if applicable how long it took, if applicable the number of days of treatment, if known the reason for the outcome and if it was an infection the outcome (recovered, death, unknown) (Table 3). These health outcomes either occur directly at the health care facility, if the facility offers inpatient care, or are reported if the patients report their outcome after a visit (e.g. by calling or re-visiting the facility). The diary consists of one table per month containing all of the different health outcomes and subcategories. Consequently, the HCWs can keep track of these outcomes with a minimal administrative effort. The local study team is still discussing if a paper table, which will be collected once a month will be used, or if alternatively, the team sends the doctor in charge once a month a mobile survey to fill in the data.

Module 5: Focus Group Discussions: The FGDs will be used to capture the common norms and beliefs of the HCWs. This tool offers many insights in shorter time compared to other qualitative methods such as participatory observation (46, 47). Data will be collected by a small local team with experience in qualitative data collection and if the security situation allows, by the Swiss TPH PhD student in autumn 2023. The team containing at least one moderator and one observer/note taker will be trained by the PhD student prior to data collection. A field research journal will be used throughout the study to take structured notes and observations of the FGDs. The discussions will be audio recorded and then transcribed into the local language and translated to French or English for further analysis.

Field notes, observation notes and focus group transcripts will be analysed using the framework method with the software MaxQDA (VERBI Software, Marburg, Germany) or NVivo (QSR International, Melbourne, Australia) (48).

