4.6 Withdrawal and discontinuation

Participants may stop their participation at any time and withdraw their consent. Local staff is recruited and employed by Tdh and has to follow the terms and conditions of the local Tdh offices which are written in their work contract.

The overall h4h project or specific project sites can be discontinued due to several reasons by the project leader, such as:

- Ethical concerns (e.g. non-acceptance of proposed technical solutions)
- Insufficient participant recruitment
- Natural hazards (e.g. heavy floods, earthquakes)
- Damage and vandalism of infrastructure, technical failure of interventions
- Alternative interventions and projects at the same facilities not coordinated with us
- Limited access by Tdh staff due to any reason out of their control including pandemics, natural hazards or deterioration of security situation
- Political constraints restricting access to the health care facilities or the project implementation

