6.1.2 Secondary hypotheses

Depending on the secondary objective, different secondary hypotheses were formed:

$H_{1.1}$ = Hygiene-related RANAS variables will differ between participants based on their demographic indicators, previous training, and the water structures available in the health care facilities.

$H_{0.1}$ = Hygiene-related RANAS variables will not differ between participants based on their demographic indicators, previous training, and the water structures available in the health care facilities.

$H_{1.2}$ = Hygiene-related RANAS variables of health care providers in the intervention facilities will be significantly better compared to the health care providers in the control facilities.

$H_{0.2}$ = Hygiene-related RANAS variables of health care providers will be the same in health care providers of intervention and control facilities.

$H_{1.e}$ = Hygiene-related health outcomes will be significantly less frequent in intervention health care facilities compared to control health care facilities.

$H_{0.e}$ = Hygiene-related health outcomes will be the same in intervention health care facilities and control health care facilities.

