6.2 Determination of sample size

To determine the required sample size, we run a series of simulation using the software R. Assuming a mean number of six staff members (range two to nine) per health facility and a mean number of five times a person was supposed to wash their hands ($SD=5$) and an intra cluster correlation coefficient of 0.15, we need to enrol 10 health facilities in each trial arm to detect difference of 15%-points in the proportion of handwashing during the five critical moments of the WHO (30% control versus 45% intervention) with 81% power at a two-sided 5% significance level. To account for potential loss to follow-up we aim to enrol in total 24 health facilities.

For Modules 1 and 3, all HCWs who are present during data collection and eligible will be asked to participate in the study. For Module 2, the observations a maximum of 10 HCWs per PHCF will be followed in order to avoid disturbing the daily routines of the PHCF too much. Module 4 follows the sample size calculation of the cRCT design, hence 24 PHCFs will be monitored. For Module 5, 6-10 FGDs will be administered and for Module 6, 10-20 interviews.

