6.3.1.1 Primary Analysis

Module 1: Combined RANAS and KAP survey: The data will be summarized using descriptive statistics. Associations of RANAS behavioural factors with good handwashing practices and health care worker's characteristics with the other outcome variables from RANAS behavioural factors will be estimated using random effect linear regression modelling and random effect logistic regression modelling. Missing data will clearly be reported but not imputed.

Module 2: Structured handwashing observations: To quantify the intervention effect logistic regression with binomial distribution with random intercepts for health care facilities models will be applied.

Module 3: Microbiological analysis of hand rinse samples: For investigating factors associated to *E.coli* and total coliform prevalence on HCWs hands, random effect linear regression models will be applied.

Module 4: Diary approach for pre-defined health outcomes: . The sum of each outcome variable separately per facility will be used as a measure for statistical analysis. To quantify the intervention effect on hygiene-related health outcomes, random effect linear regression modelling will be used.

Modules 5 and 6, FGDs and KIIs: FGDs and KIIs will be audio recorded, transcribed, and translated if necessary for further analysis. The local perception of the success and sustainability of the h4h intervention will be analysed using the framework method with the software MaxQDA (VERBI Software, Marburg, Germany) or NVivo (QSR International, Melbourne, Australia) (48).

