9.2 Risk-benefit ratio

With the h4h intervention the health care facilities will receive much needed handwashing infrastructure. An added benefit of Gravit'eau is that it only has to be refilled with water about once a month. This can save the HCWs precious time at work and water can be saved at the health care facility level to be used as drinking or cleaning water. With the Ranas behaviour change program, the HCWs will receive valuable information on how to maintain a good hand hygiene during their work. This knowledge together with the available infrastructure will enable the HCWs to better protect themselves and their patients against infections. In addition, the HCWs can transfer their knowledge to new staff or their families and communities. Finally, if the intervention helps to foster a better hygiene at health care facility level, the facility might become more attractive to patients and offer a better quality of care.

The control health care facilities will not receive any form of intervention during the the year where the intervention package is being tested in the intervention facilities. However, after this year, they will also receive an intervention package.

Depending on the Covid-19 situation in the study location, a slightly increased risk of infection arises during the FGDs. However, by conducting the FGDs outside with the use of masks and hand sanitizer and by distancing, this risk will be reduced to a minimum. In addition, the Gravit'eau does not contain water for drinking. Health effects of regular ingestion of Gravit'eau water have so far not been tested. By clearly introducing the Gravit'eau as a handwashing station and by clearly labelling the station with signs that signify "no drinking water", this risk will be reduced. During the piloting phase, the most appropriate and understandable signs will be chosen with the local staff.

To conclude, the benefits of this study for the participants, the health care facilities, and the patients clearly outweigh the potential risks for study participants. Moreover, the risk of contracting Covid-19 is already a daily risk for HCWs and might even be reduced through better access to handwashing stations.

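### Module 4 compares raw event totals per facility in a linear model with no denominator, so event risk is mixed with facility volume and time observed

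*Combined protocol and SAP*

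**What the plan says.** Section 6.3.1.1, under Module 4, defines the measure: "The sum of each outcome variable separately per facility will be used as a measure for statistical analysis". Section 4.2 repeats it for secondary endpoint C. The model follows: "To quantify the intervention effect on hygiene-related health outcomes, random effect linear regression modelling will be used". The hypothesis, in section 6.1.2, is one of frequency: "Hygiene-related health outcomes will be significantly less frequent in intervention health care facilities compared to control health care facilities".

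Section 4 describes the data source: "The diary consists of one table per month containing all of the different health outcomes and subcategories". Table 3 lists only features of each event, such as its occurrence, days, reason and outcome. Births, procedures and staff-days during follow-up are not listed, although the pilot recorded volume (Table 1, section 2.4: "Total number of births during the busiest month").

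Other sections bear on the point:

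- Section 6.2 on numbers: "Module 4 follows the sample size calculation of the cRCT design, hence 24 PHCFs will be monitored". The synopsis gives 24 facilities per country, 48 in total.
- Table 2 plans only descriptive statistics for Module 4, which conflicts with section 6.3.1.1.
- Module 4 is a secondary endpoint in section 4.2 but exploratory in sections 3.2.1 and 4.3.
- Section 4.3 refers to a proportion of reported outcomes, but only for quality control and without a denominator.
- Section 6.3.1.2 allows adjustment for confounders and baseline imbalance. Section 6.4 rules out imputation.

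**The concern.** A facility with more deliveries or a longer diary will have more events at the same risk. Randomisation turns volume differences that already exist into noise, which costs precision but does not bias the arm contrast. Stratification (section 4.3) and the adjusted analysis (section 6.3.1.2) limit chance imbalance further.

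The contrast is distorted when exposure comes to differ between arms after randomisation, and the plan itself foresees ways for this to happen. Section 9.2 says that with better hygiene "the facility might become more attractive to patients and offer a better quality of care". Section 4.6 says: "The overall h4h project or specific project sites can be discontinued due to several reasons by the project leader". Section 5.4.1 allows for facilities becoming inaccessible, and section 4.3 allows a facility to be stopped because of its outcomes. Higher attendance in the intervention arm inflates its totals and hides a benefit. Early closure of intervention sites shrinks them and suggests a benefit that is not there. Baseline adjustment cannot correct either.

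The level of the random effect is not named for Module 4. If it is the facility, as it is wherever the plan does name a level, one total per facility leaves it nothing to estimate and the model reduces to ordinary least squares.

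**Working it through.** **The plan's own figures.** The documents give no event rate, effect size or power for Module 4. The 81% in section 6.2 is for handwashing; Module 4 borrows only the number of facilities.

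**Identity.** Expected total = event risk × volume × time observed. The ratio of expected totals is therefore the risk ratio × the volume ratio × the time ratio.

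- True ratio 0.8 with attendance up 10%, 20% or 30% in the intervention arm: 0.8 × 1.1 = 0.88; 0.8 × 1.2 = 0.96; 0.8 × 1.3 = 1.04.
- No effect, 4 of 12 intervention sites stopping after 3 of 9 months: (8 + 4 × 3/9)/12 = 0.78.
- A site observed for 6 of 9 months contributes 6/9 = 0.67 of its full expected total.

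**Power by simulation.** From the plan: 24 facilities, taken as 12 per arm. Assumed, because the documents give no values: log-normal volume with CV 0.4 or 0.7, extra-Poisson SD 0.3, true rate ratio 0.6, and the event means shown. There were 4,000 trials per setting. The count model is quasi-Poisson with a log-volume offset, dispersion floored at 1 and a t reference.

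| Events per control facility | Volume CV | Linear, totals | Linear + baseline volume | Count model with offset |
|---|---|---|---|---|
| 0.3 | 0.4 | 6.0% | 6.6% | 0.2% |
| 0.3 | 0.7 | 5.7% | 7.0% | 0.4% |
| 0.8 | 0.4 | 11.8% | 12.2% | 7.3% |
| 0.8 | 0.7 | 11.6% | 13.0% | 7.9% |
| 3 | 0.4 | 29.5% | 33.1% | 33.8% |
| 3 | 0.7 | 19.6% | 30.9% | 33.0% |
| 8 | 0.4 | 43.4% | 58.1% | 63.8% |
| 8 | 0.7 | 26.1% | 54.0% | 63.0% |

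With 24 facilities per arm, 8 events and CV 0.7, the three powers are 50.7%, 87.8% and 91.2%. Type I error with equal exposure is 3.6% to 5.1% for the linear model, and 4.2% to 6.7% for the count model at 3 to 8 events.

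**Rejection with no true effect** (12 per arm, 8 events, CV 0.4):

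| Attendance, intervention arm | Linear, totals | Linear + baseline volume | Offset |
|---|---|---|---|
| +10% | 6.5% | 8.2% | 6.1% |
| +20% | 9.8% | 14.0% | 5.1% |
| +30% | 16.3% | 24.4% | 5.5% |

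With 4 of 12 intervention sites stopping after 3 months, rejection is 12.0% for totals and 5.3% with the offset.

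**Are these event counts plausible?** Median births in the busiest month are 17 to 19 (Table 1). Using that figure for all nine months gives upper limits of 17 × 9 = 153 and 19 × 9 = 171. Three events would be 3/171 = 1.8% of births, and eight would be 8/153 = 5.2%.

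**Second set of assumptions.** With 150 births per facility, 5% risk, risk ratio 0.6 and 12 per arm, power for totals is 61%, 36% and 17% at volume CV 0, 0.5 and 1.0. With the offset it is 60%, 61% and 58%.

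**The case against.** The strongest reply is that little rests on Module 4. The plan calls it exploratory, concedes in section 4.3 that it is weak because of its small sample and limited patient follow-up, and ties no primary conclusion to it. Even the better model reaches only 64% power with 12 facilities per arm. That stands, and it limits the weight of this point.

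The inputs can also be challenged. The largest gap, 26% against 63%, needs 8 events and CV 0.7. At CV 0.2 it is 59% against 66% with 8 events, and 32% against 32% with 3. For staff numbers, section 6.2's range of 2 to 9 with mean 6 caps the CV at √((9−6)(6−2))/6 = 0.58. Section 9.2 offers increased attendance only as a possibility and gives no size. Absenteeism need not scale with attendance. At +10% attendance the two analyses hardly differ. Almost all the excess rejections from higher attendance point to more events under intervention, so that route hides a benefit or suggests harm and does not produce a false claim of benefit. False benefit comes from early closure of intervention sites.

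The summing period is not stated. Monthly totals would give a facility random effect a purpose, but would still lack a denominator. The diary form is not in the text, so the absence of denominators is read from Table 3 and the description in section 4.

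None of this supplies the missing exposure or makes a raw total a measure of frequency.

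**Conclusion.** The concern holds. The planned test on totals is roughly valid when exposure is equal between arms, but it tests a different quantity from the stated hypothesis, and it loses validity for that hypothesis once exposure differs by arm.

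The loss of precision is large where facilities differ in volume and events are not rare, small where volume is even, and irrelevant below about one event per facility, where neither model is useful. Adding baseline volume to the linear model recovers most of the precision but makes the attendance distortion worse. These sizes depend on assumed event rates, volume spread and attendance changes. The missing denominator and the ratio identity do not depend on those assumptions.

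Because the module is exploratory in most of the plan, this is a change that should be made; it does not threaten the primary result.

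**What to change.** - **Model.** In sections 4.2 and 6.3.1.1, replace the linear model with a negative binomial or quasi-Poisson model of facility counts. Include arm, the randomisation strata where the number of facilities allows, and a log-exposure offset over the months observed: births for maternal, neonatal and cord outcomes, procedures for wound infection, and staff-days for absenteeism. Use a t reference: a negative binomial check gave type I error of 6% to 8% with z and 5% to 6% with t. Add a facility random intercept only if monthly counts are modelled.
- **Rare outcomes.** State that outcomes averaging fewer than about one event per facility, such as maternal death, are only described, as events and denominators by arm.
- **Data.** Add monthly births, procedures and staff-days to the diary sheet, and record the months observed.
- **Consistency.** Align Table 2 with section 6.3.1.1 and give Module 4 one status throughout. The 25% rule in section 4.3 does not define its measure. It must be reconciled with the proportion mentioned in the same section and with these denominators; no threshold is proposed here.

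The cost is SAP wording plus three totals per month, which adds some recording to a diary meant to be light. The denominators are the urgent part: the model can be changed later, but exposure not recorded at the time may be unrecoverable. Some limits remain. An offset does not cure under-reporting, may not fully correct outcome-driven stopping, and will match the events imperfectly where patients report after leaving the facility.

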6.3.1.2 Secondary Analyses

In a secondary analysis the models will be adjusted for known confounder and additional predictors imbalanced at baseline.

6.4 Handling of missing data

Because imputation of missing data in cluster randomised trials is challenging, no imputation of missing data will be done.

7 DESCRIPTION OF DATA MANAGEMENT

7.1 Specification of source documents

The source documents needed in this study are listed in the table below:

Source document	Where can the source document be found / way of collection	Storage
-----------------	--	---------

List of health care facilities	Produced during the pilot phase of the h4h project with a Facility and Evaluation Tool for WASH in Institutions	Electronic storage in password-protected secure server at Swiss Tropical and Public Health Institute and FHNW
Informed Consent Forms (ICFs)	Will be signed at the health care facility and scanned	Destruction of paper form and storage of the scan on the password-protected secure server of Terre des hommes.
Electronic case report form (CRF) for the Ranas and KAP survey	Will be collected with a password-protected tablet with automatic deletion of data after transmission to server	Electronic storage in password-protected secure server at Swiss Tropical and Public Health Institute, Switzerland and during the study duration on a password-protected Swiss TPH Laptop of the local study coordinator.
Electronic CRF for the structured handwashing observations (scenario 1)	Will be collected with a password-protected tablet with automatic deletion of data after transmission to server	Electronic storage in password-protected secure server at Swiss Tropical and Public Health Institute, Switzerland and during the study duration on a password-protected Swiss TPH Laptop of the local study coordinator.
Electronic videos of handwashing observations (scenario 2)	Will be collected with a video camera which will be collected by the Tdh research teams from the study site.	Video material will be stored electronically in a password-protected secure server at Swiss TPH, Switzerland and during the study duration on a password-protected Swiss TPH Laptop of the local study coordinator. The material on the video tape will be directly deleted after the transfer to the secure server.
Electronic CRF for the microbiological handrinse samples	Will be collected with a password-protected tablet with automatic deletion of data after transmission to server	Electronic storage in password-protected secure server at Swiss Tropical and Public Health Institute, Switzerland and during the study duration on a password-protected Tdh Laptop of the person responsible for data entry.
Paper & electronic CRF for FGDs	Will be read and moderated to the participants during the FGDs	Electronic storage in password-protected secure server at Swiss Tropical and Public Health Institute, Switzerland and during the study duration on a password-protected Swiss TPH Laptop of the local study coordinator. Paper CRF will be disposed at the study centre after the FGD.
Electronic and paper output of FGDs	Audio recordings of the FGD will be transcribed in a word file on a password-protected Tdh Laptop.	Electronic storage in password-protected secure server at Swiss Tropical and Public Health Institute, Switzerland and during the study duration on a password-

	FGD notes from the field journal will be collected	protected Tdh Laptop of the person responsible for transcription. The written paper notes will be stored in a locked cabinet at the study site.
Electronic and paper output of KIIs	Audio recordings of the KII will be transcribed in a word file on a password-protected Tdh Laptop.	Electronic storage in password-protected secure server at Swiss Tropical and Public Health Institute, Switzerland and during the study duration on a password-protected Tdh Laptop of the person responsible for transcription. Any written paper notes will be stored in a locked cabinet at the study site.
Participant identification list	Will be obtained during the baseline survey	Locked cabinet at study site (only accessible by field coordinator and the staff conducting the follow-up surveys)
Paper or electronic CRF for spot checks of Gravit'eaus	Data entry into a table on paper or an excel sheet at the study site. If previously collected on paper, the data will have to be entered into an excel sheet in a second step.	Electronic storage in password-protected secure server at Swiss Tropical and Public Health Institute, Switzerland and during the study duration on a password-protected Tdh Laptop of the person responsible for data collection. If the data is being collected on paper, storage is in a locked cabinet at the study site.
Paper CRF for the diary approach of hygiene related health outcome reporting	Data will be collected continuously in the health care facilities by HCWs on monthly sheets of paper. Once a month, Tdh staff then collects these paper sheets.	First in a locked cabinet at the health care facility and after pick up by Tdh in a locked cabinet at the Tdh office.
Electronic CRF for the diary approach of hygiene related health outcome reporting	Data will be entered from the paper CRF to an excel sheet	Electronic storage in password-protected secure server at Swiss Tropical and Public Health Institute, Switzerland and during the study duration on a password-protected Tdh Laptop of the person responsible for data entry.

